10.6 Publication Policy

The investigator shall have the right to publish the results of the study. Unless mutually agreed upon in writing, prior to submission for publication of any manuscript, poster, presentation, abstract or other written or oral material describing the results of the study, the investigator shall allow sponsor to review manuscript, poster presentation, abstract or other written or oral material which describes the results of the study for the purpose only of determining if any patentable information is disclosed. At the sponsor's request, the investigator shall withhold any publication or presentation to permit sponsor to seek patent protection and to remove any confidential information from all publications.

[figure not shown]
A series of 12 horizontal black bars of varying lengths, decreasing in length from top to bottom. Each bar is preceded by a small white T-shaped notch on the left side.

A series of seven horizontal black bars of varying lengths, each with a small white rectangular notch at its left end. The bars are arranged vertically, with the first bar being the longest and the last bar being the shortest. The lengths of the bars decrease sequentially from top to bottom.

[figure not shown]
Confidential and Proprietary

Page 21 of 27
Version 1.0, 26APR2018

[figure not shown]
Confidential and Proprietary

Page 22 of 27
Version 1.0, 26APR2018

Confidential and Proprietary

Page 24 of 27
Version 1.0, 26APR2018

Confidential and Proprietary

Page 25 of 27
Version 1.0, 26APR2018

Appendix 5

Week 12-Investigator Global Aesthetic Improvement Scale (GAIS): Compared to Baseline Photos

0	No Change
+1	Mild Improvement
+2	Moderate Improvement
+3	Significant Improvement

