3 STUDY OBJECTIVES

The objectives of this exploratory pilot study are to evaluate the safety, efficacy and ergonomics of the Cutera truSculpt RF device.

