4.1 Study Endpoints

4.1.1 Safety Endpoint

- Incidence and severity of adverse device events.

4.1.2 [REDACTED] Endpoints

- [REDACTED]
- [REDACTED].
- GAIS at 12 weeks post first and final treatment from Baseline.
- [REDACTED]
- [REDACTED]
- [REDACTED].

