4.3 Study Assessments

4.3.1 Exploratory Assessments

Subjects will undergo circumferential measurement 12 weeks post [REDACTED] final treatment visit. The difference in measurement from baseline and at 12 weeks post [REDACTED] last treatment will be calculated and reported.

An assessment of the device along with the Global Aesthetic Improvement of the subjects from baseline vs. 12 weeks post [REDACTED] last treatment.

[REDACTED]

[REDACTED]

[REDACTED]

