5.1.1 Inclusion Criteria

To be included in the study, subjects must meet all of the following Inclusion Criteria:

1. Subject must be able to read, understand and sign the Informed Consent Form.
2. Female or Male, 18 to 65 years of age (inclusive).
3. Subject has visible fat bulges in the area to be treated.
4. Non-smoking for at least 6 months and willing to refrain from smoking for the duration of the study.
5. Subject must agree to not undergo any other procedure(s) in the treatment region during the study period.
6. Subject must adhere to the follow-up schedule and study instructions.
7. Subject must adhere to the same diet and/or exercise routine throughout the study, and agree to maintain the same weight throughout the study.
8. Willing to have photographs taken of the treatment area and agree to use of photographs for presentation, (educational and/or marketing), publications, and any additional marketing purposes.
9. For female subjects: not pregnant or lactating and is either post-menopausal, surgically sterilized, or using a medically acceptable form of birth control prior to enrollment and during the entire course of the study.

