7.2 Recording AEs/ADEs and SAEs/SADEs

All AEs/SAEs or ADEs/SADEs will be: (1) evaluated and must be recorded in the subject's study case report forms (CRFs); (2) monitored and tracked from the time of the first treatment.

At each contact with the subject, the investigator must seek information on AEs/ADEs/SADEs by specific questioning and, as appropriate, by examination. AEs/ADEs/SADEs may be observed by the investigator and/or clinical research staff, elicited from the subject and/or family member or volunteered by the subject. All observed and volunteered adverse signs and symptoms, anticipated or unanticipated, regardless of severity or frequency, will be recorded in the case histories (medical chart and CRFs). Included in the description should be the nature of the sign or symptom, the date of onset, date of resolution (duration), the severity, anticipated or unanticipated, the relationship to study treatment or other therapy, the action taken (if any), and the outcome.

All SAEs/SADEs, anticipated or unanticipated, must be reported to Cutera immediately but not later than 5 working days. The SADE must be recorded in: (1) the CRF and (2) a written report must be submitted to Cutera within five (5) working days after the investigator first learns of the event and is to include a full description of the event and sequelae, in the format detailed by the Cutera Serious Adverse Event Form

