9.2 Analysis Sets

The analysis sets will include all enrolled subjects who complete treatment.

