9.3 Analysis of Efficacy/Exploratory Endpoints

Formal hypothesis testing and statistical analysis are not planned for this study.

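### As legible, the week-12 investigator GAIS form has no category below 'No Change', so the GAIS endpoint cannot show an area that looks worse than at baseline

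*Protocol*

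**What the plan says.** Section 3 makes efficacy one of the study's aims: "The objectives of this exploratory pilot study are to evaluate the safety, efficacy and ergonomics of the Cutera truSculpt RF device". Section 4.1.2 lists "GAIS at 12 weeks post first and final treatment from Baseline" among the endpoints, and the Protocol Summary also names GAIS at 12 weeks as an exploratory endpoint.

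The rating form is Appendix 5, "Week 12-Investigator Global Aesthetic Improvement Scale (GAIS): Compared to Baseline Photos". Its legible rows run upward from 0 (No Change) through +1 (Mild) and +2 (Moderate) to +3 (Significant Improvement). Row 0 follows the heading directly, and no redaction or missing-figure mark stands inside the list. No legible text says how to score an area that looks worse than in the baseline photographs.

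The other relevant statements are:
- Section 4.3.1 on size: "Subjects will undergo circumferential measurement 12 weeks post" the final treatment (part of that line is blacked out), with the difference from baseline reported.
- Section 7.2 on safety: "All observed and volunteered adverse signs and symptoms, anticipated or unanticipated, regardless of severity or frequency, will be recorded in the case histories".
- Section 9.2 on who is analysed: "The analysis sets will include all enrolled subjects who complete treatment".
- Section 9.3 on inference: "Formal hypothesis testing and statistical analysis are not planned for this study".

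**The concern.** A global improvement rating is a judgement of change, and change can go either way. A form whose lowest answer is No Change leaves the rater no answer for a worse appearance. With no hypothesis test planned, the distribution over the categories is probably what readers of the study will see, so the meaning of each category matters. A reader of the GAIS table could not tell whether subjects in the bottom category had no visible effect or had deteriorated. If raters left such items blank instead, the same reader would see only missing ratings.

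The response options are fixed on the form. A later analysis plan can decide how to tabulate them, but it cannot recover an answer that was never offered.

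**Working it through.** The plan has no figure to reproduce on this point: the 60 subjects are not derived from a calculation, and no worsening rate is given. The check is a reading of the scale followed by simple arithmetic.

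**Inputs.** Legible levels {0, +1, +2, +3} (Appendix 5); planned N = 60 (Section 9.1). The worsening share w is an assumption.

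**Step 1: where a worse-looking subject can go.** No level lies below 0, so there are two possibilities.
- *Scored 0.* Count at 0 = unchanged + worse. The data show only the sum.
- *Left blank.* Count at 0 = unchanged only, and the worse subjects join the missing ratings.

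The legible text does not say which would happen. In neither case does GAIS identify anyone as worse.

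**Step 2: how many subjects would not be shown as worse** (w × 60, illustrative):
- w = 5%: 0.05 × 60 = 3
- w = 10%: 0.10 × 60 = 6
- w = 20%: 0.20 × 60 = 12

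**Step 3: effect on summaries.**
- The number scoring +1 or more is the same in both cases. So is the proportion, as long as every assessed subject stays in the denominator. If blanks were dropped, 3 blanks would raise it by a factor of 60/57 = 1.053.
- A mean, if one were reported with worse subjects scored 0, could not fall below 0. Compared with a scale that has a −1 level it would be higher by w, for example by 0.05 at w = 5%. No legible text plans a mean.

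**Step 4: what GAIS can say about worsening.**
- *Form as legible, worse scored 0:* the worsening share is known only to lie between 0 and the No Change share. If 12 of 60 were scored 0, any share from 0% to 12/60 = 20% would fit.
- *Form with a 'Worse' row that raters use:* the share is observed. If 0 of 60 were scored worse, the exact two-sided 95% upper limit would be 1 − 0.025^(1/60) = 5.96%. Because analysis is limited to subjects who complete treatment, an assumed 54 or 48 analysed (losses of 10% or 20%) would give 6.60% or 7.40%.

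These figures show what the extra row would add. They are not evidence that worsening will occur.

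**The case against.** **The form may not be complete.** The protocol is heavily redacted, and the available text ends immediately after the +3 row. The order of the rows makes a lost row above 0 unlikely, but a 'Worse' row, a comment field or an instruction printed after +3 cannot be excluded. Places where a scoring rule might sit (Section 6, several endpoints and assessments, Appendix 6) cannot be read. This stands, and it is why confirming the form comes first. A reader might infer that the protocol certainly omits a worse category; the documents do not support that.

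**Pooling is not certain.** A reader might infer that the No Change count necessarily mixes unchanged and worsened subjects. It does so only if raters enter 0. If they leave the item blank, nothing is pooled and worsening becomes missing data. This also stands.

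**Worsening can be recorded elsewhere.** Circumference change can be positive, and adverse signs and symptoms are to be recorded whatever their severity. A reader should therefore not conclude that the study has no means of detecting deterioration. But circumference measures size rather than appearance, and no legible text makes a worse look an adverse event. Neither record separates unchanged from worse within GAIS.

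**Photographs could be graded again.** Section 5.1.1 requires subjects to be "Willing to have photographs taken of the treatment area". That may allow later re-grading, but the legible text does not say that week-12 photographs are taken. It would also be extra work that an added row makes unnecessary.

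**A one-directional scale is a legitimate choice.** For an exploratory improvement endpoint it can be defended, and the protocol contains no contradiction or wrong figure here. That limits the weight of the point. It does not remove the loss of information on an endpoint meant to inform efficacy.

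**Conclusion.** The point holds as a modest design concern. As legible, the investigator GAIS cannot show aesthetic worsening: a worse-looking area is either scored with the unchanged or lost as a blank. This rests on the legible form being complete, which has to be confirmed.

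The consequence is limited to the descriptive interpretation of one exploratory endpoint in a pilot of about 60 subjects. No error rate is involved. The result does not support a claim that the share of improved subjects is inflated: the number at +1 or more is unaffected, and the proportion moves only if blanks are dropped from the denominator. The size cannot be estimated from the protocol. The 3, 6 or 12 subjects at 5%, 10% or 20% are illustrations of an assumed rate.

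**What to change.** 1. Confirm that Appendix 5 as printed contains only the four legible categories.
2. If so, add at least one 'Worse' category below 0 before ratings are made.
3. Report the full GAIS distribution, including the number and proportion worse, and show missing ratings as their own line so that blanks are visible.

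The cost is one revised CRF page and the matching table rows. The GAIS summary may look less favourable, and some comparability is lost with any earlier use of the four-point form. No treatment, visit or eligibility rule changes.
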